TITLE: PREMATURITY AND RESPIRATORY

OUTCOMES PROGRAM (PROP)

CORE DATABASE PROTOCOL

Sponsors: NIH Grant Number:			
University of Pennsylvania Prot Number:	cocol 813839		
Principal Investigators:	for the Data Coordination	nd [name] ng Center. vestigators are listed in Section	
Clinical Trials.gov Number:	5.2.1. NCT01435187		
Original Date: Administrative Change	May 24, 2011 December 16, 2011	Version 1.0 Version 1.1	

Original Date:	May 24, 2011	Version 1.0
Administrative Change	December 16, 2011	Version 1.1
Amendment #1	October 3, 2012	Version 2.0
Amendment #2	December 17, 2013	Version 2.1

This document was prepared by the University of Pennsylvania, School of Medicine, Clinical Research Computing Unit, in the PROP Data Coordinating Center.

STUDY SUMMARY

Title	Prematurity and Respiratory Outcomes Program (PROP) Core Database Protocol
Study Design	Observational prospective cohort
Study Centers (6)	Cincinnati University Hospital, Washington University, University of California at San Francisco, Vanderbilt University, University of Rochester & University at Buffalo, and Duke University & Indiana University
Primary Hypothesis	In survivors of extreme prematurity to 36 weeks PMA, specific biologic, physiologic and clinical data obtained during the initial hospitalization will predict respiratory morbidity as defined by respiratory health care utilization and respiratory symptoms, between discharge and 1 year corrected age.
Significance	PROP will identify suitable predictors of respiratory outcome that may serve as surrogate endpoints in future trials of prevention and therapy of respiratory diseases in preterm infants.
Objectives	 To evaluate if a series of quantitative respiratory assessments performed prior to NICU discharge in extremely preterm infants will predict symptomatic respiratory disease and health care utilization during the first year of life more accurately than the current clinical or physiological diagnoses of BPD. To create a biospecimen repository for preterm infants, by collecting DNA from PROP study participants and their parents and by obtaining tracheal aspirate and urine samples from infants at pre-specified postnatal ages, that can be used to stratify patient populations based on molecular as well as clinical phenotypes. To collect detailed descriptive data on respiratory medication exposures in extremely preterm infants from birth through 1 year of age in order to understand the variability of current prescribing practice and its relationship to respiratory morbidity. To create a multi-center core database containing prospectively collected, standardized, clinical data and to test for associations between these clinical parameters and the novel, putative biomarkers with the goals of quantifying severity, refining diagnosis and prognosis, and identifying mechanisms of causation of respiratory disease in preterm infants. To assess pulmonary physiologic outcomes at 1 year of age by infant pulmonary function testing (iPFT) in a subset of infants to identify associations between standard measurements of lung function at 1 year and the quantitative and qualitative assessments of respiratory function and morbidity between 36 weeks PMA and 1 year of age.
Number of Infants	750 survivors to a postmenstrual age of 36 weeks or discharge
Main Inclusion Criteria	Gestational Age 23 0/7 – 28 6/7 weeks
Duration of Study	4 Years
Statistical Methodology	Model based and non-model based analyses, including descriptive analyses, and generalized linear mixed models (GLMM)

Table of Contents

1.	Introdu	Introduction and Background		
2.	Study Hypothesis, Objectives and Design			
2	.1.	Primary Outcome: Post-prematurity Respiratory Disease	8	
2	.2.	Specific Aims		
2	.3.	Study Population		
	2.3.1.	Inclusion Criteria		
	2.3.2.	Exclusion Criteria		
3.	Study N	Neasurements and Procedures		
3	.1.	Assessments During Hospitalization in the Neonatal Intensive Care Unit		
	3.1.1.	Daily Respiratory, Growth, and Nutrition Data		
	3.1.2.	Daily Medication Data		
	3.1.3.	Collection of Biospecimens for a PROP Repository		
3	.2.	Respiratory Assessments at 36 Weeks PMA		

	5.3.2.	Institutional Review Board46
	5.3.3.	Record Retention
5.	4.	Data Coordinating Core Responsibilities
	5.4.1.	Quality Assurance
	5.4.2.	Website47
	5.4.3.	Data Security
6.	Visit Sch	nedule
7.	Referen	ces

1. Introduction and Background

Acute and chronic respiratory morbidities are common in extremely small and preterm infants.¹ Increased survival of very premature infants is increasing the numbers of children with chronic lung disease.

The preterm birth rate in the US in 2008 was 12.3%.² Since 1990, preterm births < 34 weeks gestation have increased by 10% and late preterm births (34 to 36 weeks gestation) by 25%.² Between 20 and 35% of all extremely low birth weight infants die before their first discharge home.^{1, 3} Risk-adjusted mortality rates vary considerably between different hospitals.^{4, 5} Of those who survive the immediate neonatal period, 35-45% develop bronchopulmonary dysplasia (BPD), (Vermont Oxford Network data, 2009), when defined as need for oxygen therapy at 36 weeks postmenstrual age. The majority of infants with birth weights less than 1 kg will have a diagnosis of BPD by the Consensus Conference definition of 28 days in oxygen.⁶ BPD results from abnormal repair and impaired lung development after acute lung injury. Infants with BPD are more likely to die than those without chronic lung disease even if they survive the initial hospitalization. The odds ratio for BPD as a predictor of post-discharge mortality among 10,602 VLBW infants in the Israeli Neonatal Network was 2.4 (95% Cl: 1.4–4.2).⁷

However, the traditional categorical approach of classifying BPD as absent or present is likely an oversimplification. It is far more likely that very preterm infants develop respiratory disease across a continuous spectrum of illness severity ranging from mild to severe.⁸ Importantly, very preterm infants without a categorical diagnosis of BPD have a fairly high rate of respiratory morbidity at a corrected age of 18 to 22 months.¹ Ex-preterm infants with and without a categorical diagnosis of BPD return frequently to pediatricians, emergency rooms and pulmonologists with symptoms and signs of post-prematurity respiratory disease (PRD): intermittent or chronic wheezing, cough without cold, poor growth, apnea and cyanosis, and lower respiratory tract infections.⁹⁻¹³ More than 50% of all survivors after very preterm birth are readmitted to hospital at least once during their first 2 years of life.¹⁴ Respiratory causes account for the majority of hospital readmissions and include lower respiratory tract infection, apparent life threatening events, bacterial pneumonia and respiratory viral illness such as infection with the respiratory syncytial virus.¹⁵

Although pulmonary compliance improves over time after discharge from the NICU, very preterm infants have chronic airflow limitations that may result in airway obstruction and gas trapping throughout early childhood. Impaired lung function in premature infants can persist into adulthood, contributing to chronic respiratory diseases including asthma and emphysema. The effects of extreme prematurity on the aging lung are unknown.¹⁶

Efforts to improve the respiratory outcomes of low birth weight, fragile infants are an important public health goal. There are currently no objective measures to predict which preterm infants will have persistent respiratory problems after discharge from the hospital. The understanding of the anatomy of BPD relies on a few anatomic studies of autopsy tissues, which may not be representative of the lungs of infants who survive.^{17, 18} Furthermore, most of the available clinical and physiological information has been obtained in small series of patients who were cared for before the widespread use of antenatal steroids, postnatal surfactant, and gentle approaches to respiratory support, all of which may change the clinical spectrum of chronic respiratory disease.^{19, 20} Given the high prevalence of lasting respiratory morbidities in ex-preterm infants, strategies and tools to identify newborns at risk of low lung function and to reduce

acute and chronic respiratory morbidity are urgently needed. The intensive characterization of a large cohort of extremely preterm infants may provide the insights needed to develop a better clinical definition of BPD.

The Prematurity and Respiratory Outcomes Program (PROP) will investigate multiple research hypotheses on the molecular mechanisms that contribute to respiratory disease risk of premature neonates over the first year of life. A standardized bundle of clinical and non-invasive respiratory assessments that is tailored to the respiratory status of the infant at the time of testing will be performed near the estimated due date of very preterm infants to describe the cohort and to predict the severity of respiratory outcomes in the first year of life. It is hoped that these respiratory assessments may be sufficiently predictive to serve as surrogate endpoints in future trials of prevention and therapy.

This protocol describes a collaboratively developed multicenter prospective cohort study of very preterm infants from birth through the time of discharge from the NICU and up to 1 year of age, corrected for the degree of prematurity. Each of the 5 clinical research centers (CRC) will participate in a cooperative and interactive manner with all other CRCs, leveraging local resources and sharing biospecimens and patient data with all other collaborating sites.

The program will use the cooperative agreement mechanism and require multidisciplinary expertise including neonatologists, pediatric pulmonologists, pharmacists, and physiological, molecular, biological, biostatistical and bioinformatics scientists. Participating sites will plan and coordinate their own single-site biomarker research and will develop and implement a shared protocol for respiratory phenotyping and respiratory outcomes of extremely preterm infants. The Data Coordinating Center (DCC) will collaborate on study design, manage data collection and data monitoring and provide support for standardization of definitions, clinical report forms, and analysis.

Successful multi-center research networks require collaborative efforts, precise planning and documentation of all procedures, regular communication among all participants, and uniform adherence to the research objectives and protocol. The DCC will cultivate an atmosphere of scientific collaboration and cooperation, establish and promote effective communication, and coordinate the design, development and conduct of all multi-center protocols within the PROP. The DCC will coordinate protocol and consent form development, utilizing an administrative structure that facilitates these processes.

2. Study Hypothesis, Objectives and Design

Primary Hypothesis:

In survivors of extreme prematurity to 36 weeks PMA, specific biologic, physiologic and clinical data obtained during the initial hospitalization will predict respiratory morbidity as defined by respiratory health care utilization and respiratory symptoms, between discharge and 1 year corrected age.

2.1. Primary Outcome: Post-prematurity Respiratory Disease

The primary goal of the PROP studies (single center and multicenter protocols) is to identify biomarkers (biochemical, physiological and genetic) and clinical variables that are associated with and thus potentially predictive of pulmonary status in preterm infants up to 1 year corrected age. An objective and validated measure of pulmonary outcome at 1 year does not currently exist. Some promising measures are in development but not yet ready for use in a multi-center large clinical study. For example, reduced alveolar number is a key pathologic feature of BPD .²¹ Physiologically, this is reflected in decreased diffusion capacity of the lung to carbon monoxide (DLCO), and infants with BPD have lower DLCO compared to healthy full term controls.²² However, measurement of infant DLCO in a multi-center study is not feasible in PROP because of the lack of standardized equipment, the need for C¹⁸O instead of standard CO, and the need for a mass spectrometer to measure CO instead of a standard infrared sensor.²³

Moreover, the PROP investigators firmly believe that the burden of chronic respiratory illness on the infants and their families is of utmost importance. Therefore, we propose a composite primary outcome of morbidity that is based on serial parental reports of respiratory symptoms, medications, hospitalizations and dependence on technology during the first year of life.

Data collection for the outcome assessment will be based on interviews conducted with the infant's main caregiver at 3, 6, 9 and 12 months corrected age. The time frame for data collection is based on questions "since last contact." Numerous epidemiological studies of asthma have used parental or self report of symptoms, physician-diagnosed asthma and allergies, or the use of medications (which may abrogate symptoms) as critical outcomes.^{16, 24-26} Recent studies have most commonly employed the International Study of Asthma and Allergies in Childhood (ISAAC) questionnaire.²⁷ These studies have collected data regarding 1 year old children, although not children before one year of age. The questionnaire to be utilized in PROP has been modified from the Tucson Children's Respiratory Study (CRS)^{20, 28-31} and the Breathing Outcomes Study. The latter is an ancillary study for the NICHD Neonatal Research Network (NRN) Surfactant Positive Airway Pressure and Pulse Oximetry Trial (SUPPORT).

Survey items selected for the determination of the primary outcome will be focused on the following four domains, with any positive response to any element identifying morbidity:

- 1. **Respiratory medications**: inhaled bronchodilators, inhaled steroids, systemic steroids, methylxanthines, diuretics, pulmonary vasodilators
- 2. Hospitalizations for cardiopulmonary causes: any hospitalization regardless of duration
- 3. Symptoms: any wheeze, cough without cold
- 4. **Home technology dependence**: use of home oxygen, ventilator or CPAP/BiPAP of any durations since last contact

A late death after a postmenstrual age of 36 weeks from cardio-respiratory failure will also meet the definition of PRD.

The primary outcome will be dichotomous, and defined as "No substantial post-prematurity respiratory disease" or "Post-prematurity respiratory disease." To be classified as having post-prematurity respiratory disease, infants must have a positive response in at least 1 of 4 morbidity domains during at least 2 separate parental interviews. Quarterly data collection up to 1 year corrected age will allow us to identify phenotypes based on the trajectory of post-prematurity respiratory disease and how these different trajectories predict later lung function and the diagnosis of asthma, if we continue to follow this cohort of children.

Follow up data from recently published randomized controlled trials and observational studies in similar but not identical populations of very preterm infants suggest that the incidence of this primary outcome will be at least 30% and possibly as high as 60%.³²⁻³⁵

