3.3. Assessments During Follow-up to 1 Year Corrected Age

Research staff at the clinical PROP centers will obtain follow-up data from the infant's primary caregiver after the infant has been discharged from the hospital. This will require a significant investment of time and energy and is essential to characterize the respiratory status of study participants during the first year of life. We aim to achieve a very high retention rate of at least 90% and ideally > 95% to minimize ascertainment bias.

3.3.1. Data Collection at Months 3, 6, 9 and 12

At age 3, 6, 9, and 12 months corrected age (+ 1 month corrected age), the research staff at the clinical centers will contact the family to schedule and conduct an interview with the primary caregiver about the infant's health status. Contact information will be verified and revised as needed. A focused questionnaire will be administered over the telephone or in person at 3, 6, 9 and 12 months corrected age by the research staff to gather detailed data about hospitalizations for cardiopulmonary causes as well as for other medical reasons, respiratory medication use, respiratory symptoms and home technology dependence. For further details please refer to section 2.1

Medication used during the previous 3 months will be reported by parents to the site staff by listing them in advance of each follow-up call and reading them to the interviewer or by reading the labels to the interviewer at the time of the encounter. Exposure to environmental risk factors (young siblings, smoking, kerosene heater, pets) will also be recorded. Lastly, we will administer a symptom survey for gastroesophageal reflux disease (GERD) that was developed and validated for infants and children < 18 months by Orenstein and colleagues.⁷⁸ The 12-item questionnaire assesses symptoms associated with reflux over the past week.

3.3.2. Physical Examination at Month 12

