4.2. Primary Outcome

PROP has chosen an outcome that incorporates the elements currently considered as hallmarks of respiratory morbidity (Section 2.1). The primary outcome is dichotomous, and defined as "No substantial post-prematurity respiratory disease" or PRD. The definition of PRD for PROP requires that infants must have at least one morbidity element reported in at least 2 time frames (approximately 3 month intervals). Survey items selected for the determination of the primary outcome will be focused on four domains, with any positive response to any element identifying morbidity: respiratory medications; hospitalizations for cardiopulmonary cause; respiratory symptoms; home technology dependence; and death.

Follow up data from recently published randomized controlled trials and observational studies in similar but not identical populations of very preterm infants suggest that the incidence of this primary outcome will be at least 30% and possibly as high as 60%.³²⁻³⁵

4.2.1. **Predictors of Outcome**

The primary focus of PROP is on the delineation of early and later biomarkers during the NICU stay that predict *respiratory morbidity post discharge through 1 year of age*. The later predictive biomarkers will include various physiologic respiratory assessments described in section 3.2. Some infants will be ineligible for any of these tests, e.g. those on mechanical ventilation at 36 and 40 weeks PMA. The values for these ineligible infants for these examinations will generally be assumed to have a failure in the respective test.

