4.7.3. Missing Data

The optimal approach to missing data is assiduously avoiding it. It is likely that missing outcome data will be at or below an assumed 10% value, primarily because of mortality after 36 weeks PMA and some attrition. Nevertheless, extensive efforts will be made to collect complete one year data, with care taken to record participant primary and secondary participant contact telephone numbers and addresses, as well as reports of rehabilitation and nursing home visits, and follow-up for deaths, to death registries if necessary. If there is more than a trivial amount of missing outcome data, in secondary analyses, we will assess the impact of missing one year data. First, we will compare participants with substantially complete follow-up to those with missing one year data, with respect to observed baseline characteristics, and will pursue discrepancies to shed some light on the reasons for missing data in participants with incomplete follow-up. Second, we will investigate the impact of missingness on the estimates of effect levels and variability of effect estimates using multiple imputations.¹¹⁸

We will consider performing sensitivity analyses to assess the potential impact of missing data by fitting shared parameter models that relax the missing at random assumptions of the proposed random effects models. In addition, we shall also use inverse probability of censoring weighted methods of analysis to adjust for nonignorable dropout; when there are repeated measures of the outcome, this approach will be used in conjunction with generalized estimating equations to account for nonindependence of observations within participant.

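### The primary outcome counts positive interviews without regard to how many were completed, so read literally a missed interview can only move an infant from PRD to no PRD; and IPCW is credited with handling nonignorable dropout

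*Protocol*

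**What the plan says.** Protocol Section 2.1 bases the outcome on "interviews conducted with the infant's main caregiver at 3, 6, 9 and 12 months corrected age". It states that "The primary outcome will be dichotomous", with two classes, PRD and no substantial PRD. The rule for the first class is "infants must have a positive response in at least 1 of 4 morbidity domains during at least 2 separate parental interviews". A cardio-respiratory death after 36 weeks PMA also qualifies. Section 4.2 restates the rule as "infants must have at least one morbidity element reported in at least 2 time frames (approximately 3 month intervals"). Neither section says how an infant with fewer than four interviews is classified.

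There are two recall windows. Section 2.1 frames the questions as since last contact (the sentence beginning "The time frame for data collection is based on questions"). Section 3.3.1 says "Medication used during the previous 3 months will be reported by parents". Section 3.3 collects follow-up from the "primary caregiver after the infant has been discharged from the hospital".

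Section 4.3.4 recognises that a 3-month survey may not be done and offers a repeated-measures outcome that uses every completed survey, as a secondary analysis. Section 4.7.3 plans multiple imputation in secondary analyses, says shared parameter models will be considered, and commits to "inverse probability of censoring weighted methods of analysis to adjust for nonignorable dropout".

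**The concern.** With two classes and a threshold on the raw count of positives, whoever does not reach two positives falls into the no-disease class, whether the interviews were negative or never took place. A missed call can remove a positive but cannot add one, so any error lowers the sensitivity of the label and leaves its specificity intact. Since-last-contact recall helps only in part: after a missed call, six months of illness yield one positive interview, not two. A drug used only in the missed quarter may be lost altogether, because medication is asked for three months.

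At stake are a PRD rate that is too low, odds ratios pulled toward 1, and lost power. There is a further risk: once an infant has been given a no-PRD label, the planned imputation may never reach it, because its outcome does not look missing. Separately, a weighting analysis that is valid only under ignorable dropout could be reported as having dealt with nonignorable dropout.

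**Working it through.** **1. The protocol's own power figure.** Inputs from Section 4.4.1: 750 infants, 10% missing, PRD rate 40%, OR 1.25 per SD, two-sided alpha 0.05. N = 750 × 0.9 = 675.

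Power = Φ(√(N·p(1−p))·ln OR − 1.96) = Φ(√(675 × 0.24) × 0.2231 − 1.96) = Φ(0.88) = 81.1%.

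This agrees with the stated figure of more than 80%. The smallest OR detectable at 80% power is 1.246, so there is almost no margin.

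**2. Mislabelling by number of truly positive quarters.** Let each interview be missed independently with probability m, which is an assumption because the protocol gives no per-interview rate. If a missed quarter is simply lost, an infant with k truly positive quarters is labelled no PRD with probability P(Binomial(k, 1−m) ≤ 1).

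| m | k = 2 | k = 3 | k = 4 |
|---|---|---|---|
| 5% | 9.8% | 0.7% | 0.05% |
| 10% | 19.0% | 2.8% | 0.4% |
| 20% | 36.0% | 10.4% | 2.7% |

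For k = 2 this is 1 − (1−m)²; for example, 1 − 0.9² = 19.0%.

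**3. Across the cohort.** Each infant has a logit-normal chance of a positive quarter (SD 1.5 or 2.5, assumed), calibrated so that 40% have at least two positives out of four. Two versions were simulated: the missed quarter is lost, or its positive is carried into the next completed interview, as since-last-contact recall would allow if every domain carried over. The last column is the share of the whole cohort whose class cannot be settled from the interviews done (observed positives below two, positives plus missing at least two, missed quarter lost).

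| Interviews missed | True PRD mislabelled, quarter lost | True PRD mislabelled, carried forward | Cohort undeterminable |
|---|---|---|---|
| 5% | 3.5-4.8% | 1.8-2.5% | 5-6% |
| 10% | 7-10% | 4.1-5.6% | 10-13% |
| 20% | 16-21% | 10-13% | 23-27% |

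Medication is asked for three months only, so the truth under the written plan lies between the two versions. A beta-binomial model with within-infant correlation 0 to 0.5 gives a similar scale with quarters lost: sensitivity 93-97%, 85-93% and 71-84% at 5%, 10% and 20% missed.

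**4. Effect on the primary test.** Holding N = 675 and specificity at 1, and refitting the logistic slope to the mislabelled outcome:

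| Sensitivity of the label | Fitted OR | Power |
|---|---|---|
| 100% | 1.250 | 81.1% |
| 97.5% | 1.245 | 79.4% |
| 95% | 1.241 | 77.7% |
| 90% | 1.232 | 74.0% |
| 80% | 1.217 | 66.2% |

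Most of the power loss comes from the lower event rate and the small attenuation together; the shift in the OR alone is modest.

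**5. Long birth stays.** Interviews start after discharge. An infant for whom only the 3-month interview is impossible, and who is positive at two of the other three, is still labelled PRD if all three are done. Mislabelling is certain only when at most one interview remains possible. Because Section 3.3.1 allows ±1 month, that means a stay beyond the 9-month interview window.

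**6. The weighting claim.** Standard IPCW models the chance of remaining under observation from measured data. It removes bias when dropout is ignorable given those data. If dropout still depends on the unobserved outcome, the weights are wrong unless an explicit sensitivity parameter is added, and Section 4.7.3 names none.

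**The case against.** The strongest reply is that the protocol never says a missed interview is negative. A reader might infer such a scoring rule, but the text does not contain it: it says what PRD requires and is silent on incomplete follow-up. Sections 4.4.1 and 4.7.3 budget 10% for missing outcomes rather than calling them disease-free, and the derivation for partial follow-up could sit in the SAP, which is not at hand. This stands as a limit on the wording. It does not remove the point, because the definition that the protocol does fix has two classes, a raw count and no minimum, and no section says when partial interviews make the outcome missing.

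A reader might also infer that weighting is the plan's only answer to nonignorable loss. It is not: shared parameter models that relax missing at random are mentioned beside it, along with multiple imputation and the repeated-measures outcome. But these are secondary or only to be considered, and none sets the primary label.

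Third, it is tempting to say that the sickest, longest-hospitalised infants are systematically labelled healthy, or that their contribution is reversed. The protocol does not support that. It gives no number of infants with such stays, earlier discharges can still qualify, and the simulation uses random misses, so it shows no predictor-related bias.

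Finally, since-last-contact recall roughly halves the error at low miss rates, and with quarterly contact the two recall windows coincide. Both are right; the windows diverge only after a missed call.

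**Conclusion.** The concern holds in a limited form. As written, the primary label depends on how many interviews were completed, and the error can only run from PRD to no PRD. Under a true rate of 40%, heterogeneity SD 1.5 to 2.5 and random misses, about 2-5%, 4-10% and 10-21% of true PRD infants are mislabelled at 5%, 10% and 20% of interviews missed; the lower ends apply if recall carries a missed quarter forward. Of these inputs only the 40% is the protocol's. Sensitivity of 97.5% is enough to take the stated power just below 80%. Very long birth stays leave fewer chances to qualify, but for how many infants is unknown. The statement about IPCW in Section 4.7.3 is incorrect without a stated sensitivity parameter. This should be corrected; it does not undermine the design.

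**What to change.** 1. In Sections 2.1 and 4.2, define PRD as two or more observed positive intervals, or a qualifying late death. Define no PRD as observed positives plus missing intervals fewer than two. Otherwise the outcome is missing and is multiply imputed at interview level from the other interviews and the NICU data.
2. Reconcile the recall windows in Sections 2.1 and 3.3.1 and, after a missed call, ask about each missed quarter separately.
3. In Section 4.7.3, describe IPCW as valid when dropout is ignorable given the measured covariates, and commit to a shared-parameter or delta-adjusted imputation analysis as the nonignorable sensitivity analysis.

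I would not count respiratory support during the birth hospitalisation as a positive interval: the primary hypothesis places the morbidity between discharge and 1 year corrected age, and doing so would put predictor-period data into the outcome.

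The cost is outcome wording, one interview prompt and analysis programming. The downside is that some infants move from no PRD to missing, about 10-13% of the cohort at 10% of interviews missed under the assumptions above; asking about missed quarters separately would reduce that share.
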